4.5. Study Days and Visits

Study days are numbered relative to the first day of study drug administration. The start of treatment (Day 1) is defined as the date on which a patient takes the first dose of study drug, as recorded on the study drug diary. Days will be numbered relative to treatment start (ie, ..., -2, -1, 1, 2, ...; with day 1 being the first day of study drug administration and day -1 being the day before the first day of study drug administration).

For efficacy and safety by-visit analyses, data collected at postbaseline scheduled visits will be included using their scheduled visit, data collected at postbaseline unscheduled visits will be included and assigned to their corresponding scheduled visit, and data collected at early termination visits will be included and assigned to the next scheduled visit. After the assignments are made, if there is a scheduled and unscheduled visit at the same visit, the scheduled visit will be used in the analysis.

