3. STUDY DESIGN

3.1. General Design and Study Schema

This is a multicenter, open-label study to evaluate the safety, tolerability, and efficacy of pridopidine treatment at a dosage of 45 mg bid in adults with HD. The study will consist of a screening period up to 2 weeks, followed by an open-label treatment period.

The assessments and procedures performed during each study visit are detailed in [Table 1](#) and [Section 3.12](#).

Up to 300 patients from the PRIDE-HD and the Open-HART studies are planned to be enrolled to receive a total daily dose of 90 mg pridopidine (45 mg bid) for the duration of the study.

If medically necessary (e.g. following discussion with the medical monitor), the patient may be allowed to de-escalate to a dose of 22.5 mg bid. The start date and reason for de-escalation will be entered into the electronic case report form (eCRF).

Upon meeting eligibility criteria, patients who transition from the ACR16C015 (Open-HART) study may perform the baseline visit assessments and procedures. They do not have to undergo titration as they will continue taking the same dose as in Open-HART (45 mg bid).

Upon completion of the PRIDE-HD study and analysis of the efficacy, safety, and tolerability data, the dose of study drug administered to the patients in this long-term study may be adjusted.

After the 1 week titration period, patients will be seen at Weeks 4, 12, 26, 52, 78, and 104. An EoS follow-up visit will take place at Week 106. Safety evaluation telephone calls will be performed at weeks 18 and 38. During these phone calls, inquiries about adverse events, concomitant medication (including changes in use of benzodiazepines and antidepressants), changes in use of alcohol and illicit drugs, C-SSRS, and an abbreviated PBA-s (a subset of PBA-s questions on depressed mood, suicidal ideation, anxiety, irritability, loss of motivation, and obsessive-compulsive behaviors) will be conducted.

[figure not shown]
Patients who discontinue study medication due to safety or tolerability reasons may continue in the study off drug and perform the scheduled visits and assessments.

Patients who withdraw from the study will have the early termination procedures and assessments performed at their final visit.

An independent DSMB will oversee the study (see [Section 3.6.1](#)).

The study schema is presented in [Figure 1](#).

Figure 1: Overall Study Schema

Comments:

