3.3. Efficacy Measures and Time Points

Efficacy analyses will be considered exploratory. Comparisons will generally be made to baseline, as appropriate. Efficacy endpoints include the following:

- UHDRS-TMS - will be performed at all visits during the Open-PRIDE study.
- mPPT - will be performed at baseline and at weeks 12, 26, 52, 78, 104 and 106.
- UHDRS-TFC - will be performed at baseline and at weeks 26, 52, 78, 104 and 106.
- SF-12 (acute version) - will be administered at baseline and at weeks 26, 52, 78, 104 and 106.
- PBA-s – will be performed at all visits during the Open-PRIDE study (also part of safety assessments).
- Q-motor – will be performed at baseline and at weeks 52, 78, 104 and 106.

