3.12.3.4. Week 106 (Visit 9) - End of Study / Early Termination Visit

The following procedures/assessments will be performed at the end-of-study visit:

- perform clinical laboratory tests
- perform brief physical examination
- perform ECG
- perform vital signs measurements
- urine β -HCG test for women of childbearing potential
- C-SSRS ("Since Last Visit" version)
- UHDRS-TMS
- mPPT
- UHDRS-TFC
- SF-12 questionnaire
- PBA-s
- Q-motor
- inquire about AEs
- concomitant medication inquiry (including inquiry about changes in use of benzodiazepines and antidepressants)
- inquiry about changes in use of alcohol and illicit drugs
- PK sampling
 - PK samples will be aimed to be drawn, to the extent possible, in the event of an AE leading to discontinuation, or for patients who withdrew prematurely because of lack of efficacy.
- collect study drug
- review study compliance

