3.12.4. Procedures After Study Drug Treatment

For patients who complete the study or withdraw prematurely, final evaluations will be performed at an end-of-treatment visit or on the last day the patient receives the study drug, or as soon as possible thereafter. Procedures for patients who withdraw prematurely from the study are described in Section 4.4. As appropriate, patients should be treated with standard of care (SOC) following termination of the study.

Patients with ongoing adverse events or clinically significant abnormal laboratory test results (as interpreted by the investigator) will be monitored as described in Section 7.1.2.

Patients who discontinue study medication due to safety or tolerability reasons may continue in the study off drug and perform the scheduled visits and assessments.

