All patients will be treated with study drug during the course of the study. After the 1 week titration period, patients will be seen at weeks 4, 12, 26, 52, 78, and every 26 weeks thereafter. An EoS follow-up visit will take place 2 weeks after end of treatment visit. Safety evaluation telephone calls will be performed at weeks 18, 38, and every 26 weeks thereafter. The alternating safety visits and telephone contacts (TCs) result in a safety assessment frequency of approximately every 3 months throughout the entire study duration. The safety TCs must be conducted by the study investigator. During these phone calls, inquiries about adverse events, concomitant medication (including changes in use of benzodiazepines and antidepressants), changes in use of alcohol and illicit drugs, C-SSRS, and an abbreviated PBA-s (a subset of PBA-s questions on depressed mood, suicidal ideation, anxiety, irritability, loss of motivation, and obsessive-compulsive behaviors) will be conducted.

During the TCs, if the patient receives a score of 0 on the C-SSRS and PBA-s suicidal ideation assessments, the subsequent safety TCs will remain as scheduled as long as the scores of 0 are unchanged. If the patient receives a score of 1 or 2 on the C-SSRS or PBA-s suicidal ideation assessments, the safety TCs will be conducted every 4 weeks to monitor the patient's status until the scores change to 0 (after which the frequency of safety TCs will revert back as scheduled, as described above). Patients with a C-SSRS ideation score of 3 and above or a PBA-s suicidality

score of 3 and above, and all patients with C-SSRS suicidal attempts or acts (behavior), will be discontinued from treatment with study medication and will be referred to a psychiatrist for further evaluation and assessment, and handled as described in Section 6.1.5. of the protocol.

For patients with a C-SSRS or PBA-s score of 1 or 2, if in the judgment of the investigator, the patient is not in good mental health during an in-clinic visit or safety TC, the frequency and the methods for monitoring may be changed (ie, more frequent visits or TCs may be added as deemed necessary, or the patient can be referred to a psychiatrist for additional evaluation and treatment and will be monitored until recovery or their condition stabilizes, in accordance with the instructions provided in Section 6.1.5 and Section 7.8.1 of the protocol.

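### SAP 4.5 reports early termination data under the next scheduled visit, up to just under 26 weeks too late, in the by-visit efficacy and safety tables

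*SAP*

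**What the plan says.** SAP 4.5 sets one visit-assignment rule for efficacy and safety: "For efficacy and safety by-visit analyses, data collected at postbaseline scheduled visits will be included using their scheduled visit". Unscheduled data go to the corresponding scheduled visit. For patients who leave, "data collected at early termination visits will be included and assigned to the next scheduled visit". The section gives no day window, maximum distance or on-drug condition, and does not refer to which assessments are planned at the receiving visit. Its tie rule covers only a scheduled and an unscheduled visit falling in the same slot.

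SAP 2.1 gives the schedule: "patients will be seen at weeks 4, 12, 26, 52, 78, and every 26 weeks thereafter". Protocol 3.1 has the same visits to the end of its treatment period: "After the 1 week titration period, patients will be seen at Weeks 4, 12, 26, 52, 78, and 104". The SAP describes a larger and longer study than the supplied protocol, but the 26-week spacing is common to both.

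Not every assessment is made at every visit. Under Protocol 3.3, mPPT is first repeated at Week 12, and TFC and SF-12 at Week 26. Q-motor "will be performed at baseline and at weeks 52, 78, 104 and 106". The early termination visit shares its procedures with the end-of-study visit ("Week 106 (Visit 9) - End of Study / Early Termination Visit") and carries the full set.

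On timing relative to drug, Protocol 3.12.4 says "final evaluations will be performed at an end-of-treatment visit or on the last day the patient receives the study drug", or as soon as possible afterwards. Protocol 4.4 adds that when the final visit falls more than 7 days after the last dose, safety is assessed but efficacy is not.

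**The concern.** Assigning an early termination value to the next visit does little harm when visits are a few weeks apart. Here they are half a year apart for most of the study, in a progressive disease. A Week 53 value placed in the Week 78 row describes a patient with 25 fewer weeks of follow-up than the label says, and it adds to the Week 78 count someone who never reached that visit.

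The secondary objectives concern long-term effects, and SAP 6.2 plans no efficacy output other than actual values and changes by visit. The visit label is therefore the only time axis the reader gets. The by-visit laboratory, vital-sign and ECG summaries in SAP 7.4 to 7.6 use the same labels.

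**Working it through.** The plan states no figure for this point, so there is none to reproduce.

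**1. Largest shift.** Gaps between clinic visits from baseline to Week 104 are 4, 8, 14, 26, 26 and 26 weeks, and 26 thereafter. A visit just after Week 26, 52 or 78 is moved forward by just under 26 weeks. Before Week 26 the shift is less than 4, 8 or 14 weeks. Telephone contacts would cut the largest gap to 14 weeks if they counted as visits. However, SAP 2.1 lists them separately from visits, and the clinic measures are not taken by telephone.

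**2. Average shift.** Assume departures are spread evenly over Weeks 0 to 104. The documents give no dropout pattern.
- Within a 26-week interval: 26/2 = 13 weeks.
- Over Weeks 0 to 104: sum of squared gaps / (2 × 104) = (16 + 64 + 196 + 3 × 676)/208 = 2304/208 = 11.1 weeks.
- Moved more than 2 weeks (the widest protocol visit window is ±14 days): (2 + 6 + 12 + 3 × 24)/104 = 92/104 = 88%.
- Moved more than 13 weeks: (1 + 3 × 13)/104 = 40/104 = 38%.

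**3. Assessments not due at the receiving visit.** Take an early termination visit at Week 5.
- Read literally, SAP 4.5 sends its TFC, SF-12 and Q-motor values to Week 12, where none is planned. That row would hold only early leavers.
- SAP 6.2 defines each endpoint at the visits where it is measured. If 'next scheduled visit' is read that way, the TFC and SF-12 values go to Week 26 (21 weeks ahead) and Q-motor to Week 52 (47 weeks ahead). The limit for Q-motor is then just under 52 weeks.
- The SAP does not say which reading applies.

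**4. Effect on UHDRS-TMS.** The documents give no progression rate and no share of early termination values per visit. Assume 2 to 6 points of worsening a year and a share of 5 to 20%.
- Per displaced value, rate × shift/52: at 13 weeks, 2 × 13/52 = 0.5 to 6 × 13/52 = 1.5 points; at the 26-week limit, 1 to 3 points.
- Per visit mean, share × rate × shift/52: at 13 weeks, 0.05 × 2 × 0.25 = 0.025 to 0.20 × 6 × 0.25 = 0.30 points; at 26 weeks, 0.05 × 2 × 0.5 = 0.05 to 0.20 × 6 × 0.5 = 0.60 points.

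For scale, Protocol 1.5.1 cites an improvement of about 3 points over placebo at 45 mg bid in earlier studies.

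**5. Outputs that do not depend on the label.** Adverse event incidence and exposure-adjusted rates use event dates and exposure (SAP 7.3). Potentially clinically significant laboratory and vital-sign values use all postbaseline records (SAP 7.4, 7.5). The overall ECG finding is the worst postbaseline one (SAP 7.6). C-SSRS is summarised over the whole postbaseline period (SAP 7.8).

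**The case against.** The best defence is that the rule is prespecified, keeps observed data from leavers in the tables, and sits in a single-arm descriptive study where efficacy is exploratory. No test or error rate depends on it. That is correct and limits the weight of the point. It does not make the labels right.

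Three stronger readings are tempting, and the documents do not support them.

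- **Off-drug efficacy values passed off as long-term results.** Protocol 4.4 rules out efficacy assessment at a final visit more than 7 days after the last dose, so off-drug values are mainly a safety-data issue, where no upper limit is set. The bar is not watertight. The combined end-of-study/early termination visit lists the full efficacy battery although Week 106 is 2 weeks after end of treatment, and patients who stop drug may stay in the study.
- **Safety findings mistimed in general.** The main safety outputs listed in step 5 are untouched. Only by-visit means, changes and shifts are affected.
- **Reported progression understated by 0.5 points or more.** That is the size for one displaced value at an assumed rate. The reported quantity is a visit mean, where the effect is diluted by the share of early termination values.

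Nor is the net direction settled. The timing error alone makes a worsening disease look more stable. If patients who leave are declining faster than those who stay, keeping their values in later rows pulls the other way.

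**Conclusion.** The point holds as a labelling error in the by-visit tables. SAP 4.5 can report an early termination value up to just under 26 weeks too late. The average is about 13 weeks within the 26-week intervals and about 11 weeks over Weeks 0 to 104 if departures are evenly spread. Read literally, it also creates TFC, SF-12 and Q-motor entries at visits where they are not planned.

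The timing effect on a visit's mean TMS is modest: about 0.03 to 0.30 points at a 13-week shift and 0.05 to 0.60 at 26 weeks. Those figures rest entirely on the assumed 2 to 6 points a year and 5 to 20% share. The visit gaps come from the documents and need no assumption. The rule should be changed because these tables are the only efficacy output and the change is cheap. No formal conclusion of the study depends on it.

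**What to change.** Amend SAP 4.5 in two parts.

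1. Place an early termination value in a by-visit row only if its study day falls within a prespecified window around a scheduled visit at which that assessment is planned. Where a scheduled value exists for the same visit, keep the scheduled value.
2. Summarise all early termination values, on or off drug, in a separate row for early termination / last postbaseline value, with time since first dose and days since last dose. A row limited to on-treatment values would drop those taken after the last dose.

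The window is essential. Sending values to the nearest visit of any kind would halve the largest shift to 13 weeks and the mean to 5.5 (2304/416), but could still use visits where the assessment is not planned. Sending them to the nearest planned postbaseline visit without a limit would move Week 5 TFC and Q-motor values 21 and 47 weeks forward.

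The cost is a paragraph of SAP text, a window table and one extra row per output, with no new data. SAP 2.5.2 allows amendments to be approved before database lock. The downside is fewer values in the later visit rows, with the leavers' data shown in the separate row instead.

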5. STUDY POPULATION

5.1. General

The ITT analysis set will be used for all study population summaries. Summaries will be presented for all patients.

5.2. Patient Disposition

Patient screened, patients screened but not in the ITT analysis set (and reason not in the ITT analysis set) will be summarized using patient counts. Patients in the ITT analysis set, patients in the ITT analysis set but not treated, patients in the safety and full analysis sets, patients who completed treatment and completed study, and patients who withdraw from the treatment and study (and reasons for withdrawing) will be summarized using descriptive statistics.

5.3. Demographics and Baseline Characteristics

For demographics, the continuous variables of patient age, weight, height, and body mass index (BMI) will be summarized using descriptive statistics. The categorical variables of patient sex, race, and ethnicity will be summarized using descriptive statistics for each category. Missing categories will be presented if necessary.

For baseline characteristics, the categorical variables of CYP2D6 metabolizer genotype (poor, extensive, intermediate or ultra-rapid metabolizer), neuroleptic use, and number of cytosine-adenosine-guanine (CAG) repeats, all determined from baseline in the PRIDE-HD or HART studies, will be summarized using descriptive statistics for each category. Missing categories will be presented if necessary.

5.4. Medical History

All medical history will be coded using the Medical Dictionary for Regulatory Activities (MedDRA). The incidence of medical history abnormalities will be summarized using descriptive statistics by system organ class (SOC) and preferred term (PT). Patients are counted only once in each SOC category, and only once in each PT category.

5.5. Prior Therapy and Medication

Any prior therapy or medication a patient has had within 2 weeks prior to screening will be recorded on the CRF. The sponsor will encode all therapy and medication according to the World Health Organization (WHO) drug dictionary (WHO Drug).

The incidence of prior therapies and medications will be summarized using descriptive statistics by therapeutic class and PT. Patients are counted only once in each therapeutic class category, and only once in each PT category. Prior therapies and medications will include all medications taken and therapies administered before the first day of study drug administration.

5.6. Electrocardiography

ECG findings (normal and abnormal) at baseline will be summarized using descriptive statistics.

5.7. Study Protocol Violations

Data from patients with any protocol violations (as recorded in protocol violation CRF) during the study will be summarized overall and for each category using descriptive statistics.

6. EFFICACY ANALYSIS

6.1. General

The ITT analysis set will be used for all study population summaries unless otherwise noted. Summaries will be presented for all patients.

6.2. Efficacy Endpoint and Analysis

The efficacy endpoints are as follows:

- UHDRS-TMS change from baseline to each visit that this is measured.
- mPPT total score change from baseline to each visit that this is measured.
- UHDRS-TFC change from baseline to each visit that this is measured.
- SF-12 total score change from baseline to each visit that this is measured.
- PBA-s total score change from baseline to each visit that this is measured.
- Q-motor assessments (digitomotography, dysdiadochomotography, manumotography and choreomotography, and pedomotography) change from baseline to each visit that this is measured.

All efficacy endpoints will be summarized for actual values and changes from baseline to each visit using descriptive statistics.

PBA-s domain scores will also be summarized for actual values and changes from baseline of this study to each visit using descriptive statistics.

No formal inferential statistics will be applied to the efficacy endpoints. Efficacy analyses will be considered exploratory.

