3.10.1. Discontinuation of Individual Patients

If hypokalemia is observed, dosing will be interrupted and should not be started again until normal electrolyte values are confirmed and maintained for 7 days. Patients needing more than 14 days to reach stable potassium levels, without study drug, should be withdrawn from the study drug. The patient will be asked to continue in the study and follow the visit schedule as outlined in the protocol.

At any visit, if a QTcF of >500 msec is recorded in a single measurement, 2 additional measurements will be performed and the mean value will be calculated. If the mean value is above >500 msec, the patient should be withdrawn from the study.

If the local ECG reading results at the site match the above criterion, the patient should stop taking study medication until the central ECG reader's report is received. If the central reader does not report a QTcF interval that would lead to discontinuation according to the above, then the patient should restart study medication.

Patients should also be discontinued if:

- they experience a seizure or convulsions (regardless of the relationship to treatment);
- their body weight decreases to <50 kg (may be discontinued based on Investigator or Sponsor discretion);
- and/or if creatinine clearance decreases to <60 mL/min (calculated using the Cockcroft-Gault equation). It is allowed to repeat the test once, if clinically appropriate.
- they experience adverse event/serious adverse event of suicide ideation or attempt; or
- they have a C-SSRS suicidal ideation score >2 (ie, 3, 4 and 5); or
- they have a C-SSRS report of suicidal act; or
- they have a PBA-s suicidal ideation item score >2 (ie, 3, 4, 5) .

Patients who discontinue study medication due to safety or tolerability reasons may continue in the study off drug and perform the scheduled visits and assessments.

In case the 45 mg bid treatment arm in PRIDE-HD is discontinued for safety reasons, the Open-PRIDE-HD study (utilizing the same 45 mg bid dose) will be stopped.

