6.1.5. Problem Behaviors Assessment-Short Form

Because of the prominence of psychiatric symptoms in HD, it is recommended that the PBA-s form be used in all HD studies with any need for behavioral assessment as a comprehensive screen for the most common psychiatric symptoms in HD (Craufurd et al 2001; Kingma et al 2008). The PBA-s also includes questions concerning suicidal behavior, a particular concern in HD. The PBA-s is based on the same set of core behavioral symptoms as the UHDRS Behavioral questions, which were used previously as the global psychiatric measure in most HD studies. The PBA-s has more detailed questions and more specific guidance on administration and scoring.

The PBA-s is a brief semi-structured interview covering the most common behavioral and psychiatric manifestations of HD. The interview is not restricted to a single construct, but rather covers several broad symptom domains relevant to HD, comprising 11 items: low mood, suicidal ideation, anxiety, irritability, anger/aggressive behavior, loss of motivation, perseverative thinking or behavior, obsessive-compulsive behaviors, paranoid thinking, hallucinations, behavior suggestive of disorientation. Each symptom is rated for severity on a 5-point scale according to detailed scoring criteria which roughly correspond to the following: 0 = “not at all”; 1 = trivial; 2 = mild; 3 = moderate (disrupting everyday activities) and 4 = severe or intolerable. Each symptom is also scored for frequency on a 5-point scale as follows: 0 = symptom absent; 1 = less than once weekly; 2 = at least once a week; 3 = most days (up to and including some part of every day); and 4 = all day, every day. Severity and frequency scores are multiplied to produce an overall ‘PBA score’ for each symptom.

Only the abbreviated PBA-s (i.e. items of the PBA-s relevant to suicidality [depressed mood, suicidal ideation, anxiety, irritability, loss of motivation, obsessive-compulsive behaviors]) will be collected during the additional safety TC. If the patient has a positive score 1 and 2 on the suicidal ideation item or depressed mood item of the PBA-s, the patient will be monitored more closely and treated according to the investigator's medical judgment. Patients with C-SSRS or PBA-s suicidality scores 1 and 2 may be handled by study investigator/neurologist with a consultancy with psychiatrists where necessary per investigator’s medical judgement.

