1.2. Study Endpoints

1.2.1. Safety Endpoints

The safety endpoints for this study are as follows:

- adverse events (AEs) throughout the study
- vital signs assessments
- concomitant medication usage throughout the study
- physical examination findings
- clinical laboratory evaluations (hematology, clinical chemistry, and urinalysis)
- electrocardiogram (ECG) findings
- Suicidality [using the Columbia-Suicide Severity Rating Scale (C-SSRS)] and Problem Behaviors Assessment-Short form (PBA-s)

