4. GENERAL ISSUES FOR DATA ANALYSIS

4.1. General

Descriptive statistics for continuous variables include n, mean, standard deviation (SD), standard error (SE), median, minimum, and maximum. Descriptive statistics for categorical variables include patient counts and percentages, missing category will be displayed as appropriate.

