4.3. Scoring for Rating Scales

A detailed description for all rating scales below can be found in the protocol.

The UHDRS comprises a broad assessment of features associated with HD. It is a research tool which has been developed to provide a uniform assessment of the clinical features and course of HD. The TMS component of UHDRS comprises 31 assessments from the 15 items of the UHDRS. The UHDRS-TMS is calculated as the sum of the 31 motor assessments.

The mPPT quantifies the patient's performance in physical tasks. It is a standardized 9-item test that measures the patient's performance on functional tasks. Both the speed and accuracy at which the patients complete the items are taken into account during scoring. The maximum score of the test is 36, with higher scores indicating better performance. The mPPT total score calculated as the sum of the 9 items. See [Appendix A](#) for details of the scoring method for the mPPT total score.

The TFC scale of the UHDRS assesses 5 functional domains associated with disability (occupation, finances, domestic chores, activities of daily living, and care level). Scores on each item range from 0 to either 2 or 3 (eg, Occupation: 0 = unable, 1 = marginal work only, 2 = reduced capacity for usual job, 3 = normal). The 5 items are summed to yield a TFC total score, which ranges from 0 to 13, with greater scores indicating higher functioning.

The SF-12[®] is a multipurpose short-form generic measure of health status. The 12 items in the SF-12[®] are a subset of those in the SF-36[®]; SF-12[®] includes 1 or 2 items from each of the 8 health concepts. The SF-12[®] total score is calculated as the sum of the 12 items.

The PBA-s is a brief semi-structured interview covering the most common behavioral and psychiatric manifestations of HD. The interview is not restricted to a single construct, but rather

covers several broad symptom domains relevant to HD, comprising 11 items. Each symptom is rated for both severity and for frequency on a 5-point scale. Severity and frequency scores are multiplied (after setting all values outside the range of 0-4 to missing) to produce an overall 'PBA score' for each symptom. The PBA total score is the sum of all PBA scores across the 11 symptoms.

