7.6. Electrocardiography

Shifts (normal and abnormal) from baseline to overall finding and each visit will be summarized using patient counts. For overall finding, the summary will use the worst postbaseline finding for the patient (the abnormal finding if there are both normal and abnormal findings). Summary statistics for ECG variables will be presented at baseline and each visit. Actual values and changes from baseline to each visit will be summarized using descriptive statistics.

The incidence of potentially clinically significant abnormal values for ECG variables will be summarized using descriptive statistics with the criteria specified below.

- QTcF values >450 msec or >480 msec or >500 msec.
- QTcF change from baseline values >30 or >60.
- PR change from baseline ≥25% and value >200.
- QRS change from baseline ≥25% and value >110.
- Heart rate value <60 bpm or >100 bpm.

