7.8. Other Safety Assessments

Summary statistics for the C-SSRS baseline version will be presented at screening. Patients with suicidal ideation and behavior items will be summarized as categorical data using descriptive statistics.

Summary statistics for the C-SSRS last visit version will be presented at overall postbaseline. Patients with suicidal ideation and behavior items will be summarized as categorical data using descriptive statistics.

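### PBA-s is a declared safety endpoint, but no planned PBA-s table counts patients who worsened or uses a patient's worst postbaseline value

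*SAP*

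**What the plan says.** SAP 1.2.1 names as one safety endpoint "Suicidality [using the Columbia-Suicide Severity Rating Scale (C-SSRS)] and Problem Behaviors Assessment-Short form (PBA-s". SAP 1.2.3 also lists PBA-s under efficacy and notes that it is part of the safety assessments too. Safety and tolerability are the primary objective (SAP 1.1).

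SAP section 7 covers exposure, adverse events, laboratory tests, vital signs, ECG, concomitant medication and other safety assessments. The last of these, section 7.8, deals only with the C-SSRS: "Summary statistics for the C-SSRS last visit version will be presented at overall postbaseline", with ideation and behaviour summarised as categories. PBA-s is not mentioned anywhere in section 7.

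The planned PBA-s output is in SAP 6.2: total score by visit, and "PBA-s domain scores will also be summarized for actual values and changes from baseline of this study to each visit using descriptive statistics". SAP 4.1 explains the term: "Descriptive statistics for continuous variables include n, mean, standard deviation (SD), standard error (SE), median, minimum, and maximum". On scoring, SAP 4.3 says "Severity and frequency scores are multiplied (after setting all values outside the range of 0-4 to missing) to produce an overall" score per symptom. Protocol 6.1.5 anchors the upper severity grades as "3 = moderate (disrupting everyday activities) and 4 = severe or intolerable".

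The protocol acts on individual PBA-s values. Section 3.10.1 discontinues patients if "they have a PBA-s suicidal ideation item score >2". Sections 6.1.5 and 7.8.1 require psychiatric referral for a significant rise on the suicidality scale, giving 2 points or more as the example.

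**The concern.** A safety reader wants to know how many patients got worse, and how badly. A mean or median change by visit does not answer that, because a minority who deteriorate can be diluted by stable patients or cancelled by improvers. By-visit displays also do not follow one patient to his or her worst value. The plan does this for ECG: "For overall finding, the summary will use the worst postbaseline finding for the patient". For PBA-s, the report could not say how many patients moved to moderate or severe low mood, irritability or anxiety during the study. It also could not say directly how many met the protocol's own PBA-s trigger.

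**Working it through.** The plan states no figure to reproduce. The check compares the planned displays, then asks what the PBA-s displays can and cannot show.

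**1. Planned displays side by side**

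| Measure | SAP section | Patients counted? | Worst or any postbaseline value used? |
|---|---|---|---|
| Adverse events | 7.3 | Yes | Yes, greatest severity |
| Laboratory tests | 7.4 | Yes, shifts and incidence | Incidence uses all postbaseline values, unscheduled included |
| Vital signs | 7.5 | Yes, incidence | Same |
| ECG | 7.6 | Yes, shifts and incidence | Shift uses worst finding |
| C-SSRS | 7.8 | Yes, categorical | Overall postbaseline |
| PBA-s | 6.2 only | No, 0 of 11 items | No |

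Physical examination findings also lack a table of their own. However, Protocol 7.6 makes any clinically significant worsening an adverse event, so those are counted.

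**2. What the by-visit statistics reveal.** These inputs are assumed for illustration and are not trial data: *k* of *N* patients go from 0 to 9 on one symptom (severity 3 × frequency 3) and the rest do not change. Mean change = 9*k*/*N*.

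- *N* = 300 (protocol maximum), *k* = 6, 15, 30 (2%, 5%, 10%): 54/300 = 0.18, 135/300 = 0.45, 270/300 = 0.90.
- *N* = 650 (SAP maximum), *k* = 13, 32, 65: 117/650 = 0.18, 288/650 = 0.44, 585/650 = 0.90.
- The median is 0 in all six cases. If equally many patients improve by 9, the mean is 0 as well.

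The SD does respond (1.26, 1.96 and 2.70 for the three cases at *N* = 300), and the maximum shows the single worst value. Neither can be turned into a count.

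**3. Which values reach the displays**

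- SAP 4.5 uses the scheduled value when a scheduled and an unscheduled value fall at the same visit. PBA-s is collected at unscheduled visits made for psychiatric adverse events (Protocol 3.12.5), so a worse value can drop out.
- Telephone contacts collect 6 of 11 items. Missing share = 5/11 = 45%, above the 25% limit in SAP 4.4, so those contacts yield no total score.
- SAP 6.1 assigns the ITT set to its summaries. Protocol 9.7 places safety analyses on the safety set.

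**4. What the score itself hides.** Severity 3–4 with frequency 1–4 gives products 3, 6, 9, 12, 4, 8, 12, 16. Severity 1–2 gives 1, 2, 3, 4, 2, 4, 6, 8. The products 3, 4, 6 and 8 occur in both lists. A move from mild all day (2 × 4 = 8) to severe weekly (4 × 2 = 8) is a change of 0. A table of severity avoids this.

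**5. What other tables capture.** Suspected suicidality must be reported as an adverse event and stops drug (Protocol 7.1.1, 7.1.6). It therefore appears in SAP 7.3, in withdrawal reasons (5.2) and usually in the C-SSRS table (7.8). A new treatment for a worsening condition puts that condition on the adverse event form (Protocol 5.3). Deterioration of Huntington symptoms otherwise counts as an adverse event only if it exceeds that patient's expected course (Protocol 7.1.1). The uncounted remainder is mainly non-suicidal worsening judged to be expected and not newly treated. A PBA-s ideation trigger without a C-SSRS finding or adverse event would be visible only as a treatment withdrawal.

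**6. The meaning of *score*.** Protocol 3.10.1 glosses a score above 2 as 3, 4 or 5. Severity runs 0–4, and no product of two whole numbers from 0 to 4 equals 5, so neither reading fits. Any count needs the term defined.

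**The case against.** PBA-s is analysed. It has an acknowledged dual role, 6.2 gives it a domain-score summary that no other scale receives, and the minimum and maximum are shown. Its declared safety role is mainly suicidality, which adverse events, the C-SSRS and withdrawals largely cover. The protocol deliberately keeps expected Huntington deterioration out of adverse events, so leaving that to score summaries is defensible. SAP 6.2 does not itself say that the scores are continuous, and *domain score* is undefined. Protocol 9.7.2 promises counts for categorical variables.

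Much of this stands and narrows the point. It does not remove it. Actual values with changes from baseline indicate continuous summaries, and no reading yields a defined category of worsening. Protocol 9.7.2 names no PBA-s category, and the SAP prevails where the two differ. The suicidality boundary is also not sharp: Protocol 6.1.5 describes depressed mood, anxiety and irritability as items relevant to suicidality.

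A reader might infer three stronger things that the documents do not support:

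- That suicidality goes uncounted. Step 5 shows that most of it is counted elsewhere.
- That half of moderate or severe worsening would be hidden, because 4 of the 8 severity 3–4 pairs share a product with severity 1–2. That counts cells of the scale. It says nothing about patients, and the product is the scoring the protocol specifies.
- That counts would show harm from pridopidine. In a progressive disease without a control arm they cannot.

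**Conclusion.** The point holds as a reporting gap of moderate weight. A declared safety endpoint, under a primary objective of safety, has no patient-level result on any of its 11 items. The gap is mainly non-suicidal behavioural worsening judged to be within the expected disease course, plus ideation triggers seen only on PBA-s. How many patients this concerns cannot be estimated from the documents, and the figures in step 2 are illustrations.

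This rests on two assumptions. First, the PBA-s scores in 6.2 are summarised as continuous variables. Second, the PBA-s rules in the protocol at hand still apply in the version the SAP follows. The SAP's maximum of 650 patients, against 300 in this protocol, suggests a later amendment, but SAP 2.1 repeats the threshold of 3 for PBA-s suicidality. The omission itself is certain; its practical consequence is less so.

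**What to change.** Add to SAP 7.8, on the safety analysis set:

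1. For the suicidal ideation item, the number and percentage of patients with any postbaseline severity of 3 or above, and with a rise of 2 points or more from baseline. State that *score* means severity, 0–4. These follow the protocol's own stopping threshold and its referral example, so no new cut-off is needed.
2. For each of the 11 items, a shift table from baseline severity to worst postbaseline severity, including unscheduled and early-termination values and, for the 6 abbreviated items, telephone values.

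Show Open-HART patients separately. They enter without washout on 45 mg bid, so their baseline in this study is on drug. SAP 4.2 instead sets their general baseline before Open-HART dosing. State whether values after stopping drug are included, since patients may stay in the study off drug.

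The cost is SAP wording and two descriptive displays from data already collected, with no new assessments; SAP 2.5.2 provides for SAP amendments approved before database lock. The drawback is interpretive and should be printed with the tables. Worst-value counts grow with length of follow-up and with contact frequency (calls every 4 weeks for patients with ideation scores of 1 or 2), include transient changes, and cannot be attributed to drug.
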